9.5 Post Treatment Follow-Up

All subjects will be followed for 2-3 weeks after the final application of DPCP Ointment. All protocol-defined AEs occurring in treatment periods should be fully evaluated by the Investigator and recorded on the appropriate Adverse Event Report (Appendix C) documented in the subjects' files.

Subjects who prematurely discontinue from the study will be encouraged to follow up 6 weeks following their last dose.

9.6 Post Adverse Event Follow-Up

All subjects with AEs will be followed until the event resolves or until participation in the study ends. Resolution of those deemed probably related to the administration of the DPCP Ointment will be followed until the events resolve or until the Investigator judges the event to be “chronic” or “stable.”

9.7 Laboratory Tests

Blood specimens for hematology and chemistry will be collected at the Screening Visit, week 12, and at the Follow-up Visit (Week 18 +3d) for all subjects. The following tests will be performed:

Laboratory Tests	
Hematology	Chemistry
Hemoglobin	Sodium
Hematocrit	Potassium
Platelets	Chloride
WBC	Bicarbonate
	BUN/Urea
	Creatinine
	Total protein
	Albumin
	Alkaline phosphatase
	AST (SGOT)
	ALT (SGPT)
	Calcium
	CRP

Sample collection, handling, labeling, and shipping should be conducted following the instructions provided by the relevant certified laboratory and the applicable local regulations.

The investigator will review the subjects’ laboratory reports in a timely manner. Screening laboratory abnormalities viewed as clinically significant by the investigator that do not exclude the subject from study participation will be documented in the subject’s medical record. The investigator will complete an appropriate AE form for any new or worsening abnormal test results that are identified as clinically significant after baseline. If a subject experiences a cardiovascular or hematologic event (including laboratory abnormalities), Grade 2 or higher, the study drug will be discontinued.

AEs that may be associated with venipuncture include:

- Pain
- Bruising
- Bleeding at the puncture site
- Fainting
- Inflammation of the vein

10. STATISTICAL METHODS

10.1 Data to be Analyzed

Data will be analyzed for efficacy. For primary endpoint analysis, subject data will be analyzed up to the point in which compliance is maintained.

Subjects missing > 2 consecutive treatment sessions or 20% of treatment visits in total will not be included in subsequent analysis and will not be eligible to continue receiving DPCP therapy through our center.

10.2 Determination of Sample Size

Statistical considerations

The primary endpoints ranked below in order of importance are as follows:

1. The proportion of **subjects** who have $\geq 75\%$ or $\geq 50\%$ decrease in their SALT score (SALT₇₅ and SALT₅₀, respectively), as compared to baseline at the completion of the study or at any time during the study.
2. Subject assessment of total scalp hair regrowth or loss using a visual analog scale and Investigator assessment of the total SALT score.

The proportion of subjects with $\geq 75\%$ or $\geq 50\%$ decrease in the SALT score will be described using the fraction achieving the desired decrease and the associated confidence interval, computed using the exact Agresti-Coull method. To describe change in SALT score, we will use the average change and associated confidence interval.

For a total sample size of 10 participants we anticipate 6 or 8 providing the primary outcomes. For changes in the binary outcomes, i.e., proportions having $\geq 75\%$ or $\geq 50\%$ decrease in their SALT score, the 95% confidence interval for this proportion is as follows for each possible outcome:

- 6 participants providing data: 0 of 6 meeting the criterion gives an interval of 0 to 0.44; 1/6, 0 to 0.58; 2/6, 0.09 to 0.70; 3/6, 0.19 to 0.81; 4/6, 0.30 to 0.91; 5/6 0.42 to 1; and 6/6, 0.56 to 1.
- 8 participants providing data: 0/8, 0 to 0.37; 1/8, 0 to 0.49; 2/8, 0.06 to 0.60; 3/8, 0.13 to 0.70; 4/8, 0.22 to 0.78; 5/8 0.30 to 0.87; 6/8, 0.40 to 0.94; 7/8, 0.51 to 1; and 8/8, 0.63 to 1.

Exploratory Endpoints

The primary outcomes for the analysis are levels of T-cell and DC markers. We will compute confidence intervals and do paired t-tests for changes in these measures. These analyses will most likely use the logarithms of these measures, as is commonly done; the decision to use or not use logarithms will be based on preliminary analyses.

For change in a participant's rating of hair loss using a visual analog scale, the confidence interval width is $2 \times [97.5\text{th percentile of the t distribution}] \times \text{the standard deviation of a single measurement} / \text{square-root (sample size)}$. For 6 and 8 participants, the 97.5th percentiles are

2.57 and 2.36. Thus, the respective confidence interval widths are 2.1 standard deviations and 1.7 standard deviations. We currently lack information needed to supply a standard deviation describing variation between persons in the change in this VAS rating; one of the goals of this pilot study is to collect this information.

To estimate power, preliminary data were obtained from a pilot study (Fuentes-Duculan et al. Abstract, ISDS, November, 2014). Confidence interval widths are computed as above.

Assuming the standard deviations are as reported in that abstract, and that the analyses are done on the common logarithm scale as in the abstract and analyses are done on the common-log scale, the confidence interval widths re-expressed on the original (i.e., non-logarithmically transformed) scale are 46-fold and 20-fold differences for 6 and 8 subjects respectively. For tests, again assuming the standard deviations are as reported in that aforementioned abstract, for 6 and 8 participants with data we have 80% power to detect a 14-fold change (using two-tailed alpha = 0.05).

For the analysis of various biopsy parameters, [name] will be supported a statistician in his group.

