Statistical Considerations	
Statistical Considerations: The proportion of subjects with $\geq 75\%$ and $\geq 50\%$ decrease in the SALT score (at any time during treatment; endpoints 1 and 2) will be described using the fraction achieving the desired decrease and the associated confidence interval, calculated by the Agresti-Coull exact method. To describe change in SALT score, we will use the average change and associated confidence interval.
 
Statistical power: For a total sample size of 10 we anticipate 6 or 8 participants providing data. For changes in binary outcomes, for 6 participants, the Agresti-Coull 95% confidence intervals for the proportion having an effect range in width from 0.44 (0 to 0.44 if 0 of 6 have an effect or 0.56 to 1 if 6 of 6 have an effect) to 0.62 (i.e., 0.19 to 0.81 if 3 of 6 have an effect). For 8 participants, the Agresti-Coull 95% confidence intervals for the proportion having an effect range in width from 0.37 to 0.56.

Exploratory Endpoints

To identify scalp skin biomarker profiles that characterize a response to DPCP treatment, enabling future potential for predicting individual responses to treatment and the likelihood of a sustained response. The primary outcomes for this analysis are levels of T-cell and DC markers, which will be analyzed using paired t-tests. To estimate power, preliminary data were obtained from a pilot study (Fuentes-Duculan et al. Abstract, ISDS, November, 2014). Assuming the standard deviations are as reported in that abstract, for comparing pre- vs. post-treatment, for 6 participants we have 80% power to detect a 14-fold change (using two-tailed alpha = 0.05); for 8 participants the detectable difference is 8-fold. For the analysis of various biopsy parameters, [name] will be supported by a statistician in his group.

For the change in subject VAS score, the confidence interval width will be 2.1 standard deviations for 6 participants and 1.7 standard deviations for 8 participants; we lack information needed to supply a standard deviation describing variation between persons in this change.

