8.2 Exploratory Endpoints

To identify scalp skin biomarker profiles that characterize a response to DPCP treatment, enabling the future potential for predicting individual responses to treatment and the likelihood of a sustained response with the opportunity to study blood samples in the future if needed.

Subject assessment of hair loss/growth with the subject hair loss assessment and investigator assessment of the total SALT score.

Gene expression and histologic analysis (immunohistochemistry) on skin biopsy specimens will be done. mRNA will be prepared from skin samples stored frozen in RNA Later solution. Expression of cytokine genes that define different polar sets of T-cells will be measured: interferon-gamma, IL-13, IL-17A, IL-22, IL-9, IL-32; other inflammation associated genes such as IL-12, IL-23, IL-1B, and IL-15 will also be measured. mRNAs for a series of negative immune regulatory genes, e.g., Foxp3, CTLA4, PD-1, etc. will be measured by RT-PCR. Re-initiation of hair growth will be assessed by measuring expression of mRNAs encoding hair-associated keratins and keratin-associated proteins. A subset of patients showing good responses of hair re-growth will be selected for whole transcriptome analysis. Pre and post-treatment lesional biopsies will have global mRNA profiles established using Affymetrix U133 2.0Plus arrays. From frozen samples in OCT blocks, frozen sections will be prepared that will be stained initially with antibodies to T-cells (CD3, CD8), dermal dendritic cells (CD11c), and the regulatory marker Foxp3. Once the gene expression analysis is completed, expression of negative immune regulatory proteins will be examined, as guided by the genes with highest up-regulation in post-treatment samples in patients with good hair regrowth.

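### Section 10.2 tests an unlisted set of scalp markers one by one, with power quoted for a single marker and no false-discovery control, although the exploratory aim is to identify marker profiles

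*Combined protocol and SAP*

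**What the plan says.** The biomarker aim in section 8.2 begins: "To identify scalp skin biomarker profiles that characterize a response to DPCP treatment". Its stated purpose is to open the way to predicting individual response in future.

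The method is in section 10.2 under Exploratory Endpoints. The outcomes are defined only as a class: "The primary outcomes for the analysis are levels of T-cell and DC markers". The analysis is: "We will compute confidence intervals and do paired t-tests for changes in these measures". The Study Summary says the same: "The primary outcomes for this analysis are levels of T-cell and DC markers, which will be analyzed using paired t-tests".

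Section 8.2 lists the assays:
- Six T-cell cytokine genes: "Expression of cytokine genes that define different polar sets of T-cells will be measured: interferon-gamma, IL-13, IL-17A, IL-22, IL-9, IL-32".
- Four further inflammation genes (IL-12, IL-23, IL-1B, IL-15), given as examples.
- Three negative regulators (Foxp3, CTLA4, PD-1), also given as examples.
- Four stains (CD3, CD8, CD11c, Foxp3).
- An unnumbered set of hair keratins, and whole-transcriptome arrays in a subset of good responders.

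Alpha 0.05 appears only where power is discussed. The Study Summary says "for 6 participants we have 80% power to detect a 14-fold change (using two-tailed alpha = 0.05") and "for 8 participants the detectable difference is 8-fold". Section 10.2 instead gives 14-fold for both 6 and 8 participants. It also gives the precision expected: "the confidence interval widths re-expressed on the original (i.e., non-logarithmically transformed) scale are 46-fold and 20-fold differences for 6 and 8 subjects respectively".

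The documents contain no multiplicity adjustment, lead marker or closed marker list, and no statement that the marker p-values are descriptive.

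**The concern.** The aim is to identify markers, and the only inferential tool stated is one test per marker. With 6 to 8 pairs and a dozen or more tests, some raw p-values below 0.05 are to be expected by chance, and nothing in the plan tells a reader how to discount them. Because the tested set is not written down, it could also be settled after the data are seen. Whether logarithms are used is already left to preliminary analyses.

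The stated 80% power is correct for one marker considered alone. Printed without that qualification, it can be read as describing the search across markers. What is at stake is a short list of markers carried into later studies as findings when some of them may be chance.

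**Working it through.** **Inputs.** From the documents: n = 6 or 8; interval widths of 46-fold and 20-fold; detectable changes of 14-fold (n = 6) and 8-fold (n = 8, Study Summary); two-tailed alpha 0.05; the assay list in section 8.2. Assumed, because the documents give no figure: equal correlation between markers of 0 to 0.7.

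**1. The plan's own figures.** Interval width in SD units is 2 × t(0.975, n−1)/√n.
- n = 6: 2 × 2.571/√6 = 2.10 SD.
- n = 8: 2 × 2.365/√8 = 1.67 SD.

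These match the stated 2.1 and 1.7. The implied SD of the log10 change is log10(46)/2.10 = 1.663/2.099 = 0.79, and log10(20)/1.67 = 1.301/1.672 = 0.78. I use the middle value, 0.785.

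The noncentral t distribution gives 80% power at a standardised change of 1.435 (n = 6) and 1.156 (n = 8):
- n = 6: 10^(1.435 × 0.785) = 13.4-fold, against 14 stated.
- n = 8: 10^(1.156 × 0.785) = 8.1-fold, against 8 in the Study Summary.

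The stated power is therefore that of one unadjusted test. A 14-fold change at n = 8 would have about 94% power, so the section 10.2 sentence giving 14-fold for both sizes does not agree with the Study Summary.

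**2. Number of markers.** 6 + 4 + 3 = 13 mRNAs, plus 4 stains, makes 17 assays. Foxp3 is in both groups, so there are 16 distinct markers.

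**3. Chance of at least one p < 0.05 when nothing changes.** For k independent tests this is 1 − 0.95^k:
- k = 17: 58.2%.
- k = 16: 56.0%.
- k = 9: 37.0% (the number of T-cell and dendritic-cell markers named in the Introduction, which the plan does not say is the analysis list).
- k = 4: 18.5%.

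Simulated paired t-tests (40,000 runs per cell; each range covers n = 6 and n = 8):

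| Tests | Corr. 0 | 0.3 | 0.5 | 0.7 |
|---|---|---|---|---|
| 16–17 | 55–58% | 49–51% | 41–43% | 30–33% |
| 9 | 37% | 34% | 29–30% | 23% |
| 4 | 19% | 18% | 16% | 14% |

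The expected number of false positives is 0.05k whatever the correlation: 0.80 for 16 tests, 0.85 for 17. With Benjamini-Hochberg at 5%, the chance of any rejection under no change was about 4–5% in every 16- and 17-test setting.

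**4. Cost of a binding adjusted threshold.** I simulated 16 and 17 markers of which 4 or 8 (about a quarter or a half) truly change by 14-fold at n = 6 or 8-fold at n = 8, with log10 SD 0.785 and correlation 0 to 0.5. Raw per-marker power was about 80%. Power after Benjamini-Hochberg was about 36–42% with 4 true changes and 51–56% with 8.

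**The case against.** The strongest objection is that this is an exploratory endpoint in a pilot of up to 10 subjects, and no decision in the trial rests on it. That stands. It is why the point concerns reporting and does not call for formal error control.

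A reader might infer more than the documents support in three ways.
- *That markers are selected by p < 0.05.* No such rule is written. The one written follow-up choice, in section 8.2, picks proteins by the size of gene up-regulation in patients with good regrowth.
- *That at least 17 markers are tested, so a false positive appears about half the time.* Section 10.2 ties the t-tests to T-cell and dendritic-cell markers, and no section assigns the general inflammation or regulatory genes to that class. The set could be as small as the four stains. *About half* also needs low to moderate correlation, which is not given.
- *That the arrays add thousands of such tests.* No section says that array transcripts receive paired t-tests.

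It is also fair that a complete absence of change is unlikely: the Introduction cites about 7,500 transcripts modulated at peak in healthy volunteers given DPCP. That does not protect the markers that do not change. If 8 of 16 were unchanged, independent tests would still give at least one false positive with probability 1 − 0.95^8 = 34%.

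Lastly, a paired pre/post test shows change on treatment. It does not show association with regrowth, and adjusting p-values does not alter that.

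**Conclusion.** The gap is real and modest. The tested markers are not listed, the power is per marker without saying so, and nothing is said about multiplicity. Its size depends on which markers are tested and how correlated they are, and the documents settle neither. For all 16–17, the chance of at least one p < 0.05 with no true change is about 41–58% at correlations of 0 to 0.5 and about 30–33% at 0.7. For the four stains alone it is about 14–19%. Every one of these readings is well above 5%.

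The documents do not support saying that the plan picks markers on unadjusted significance, or that a false marker is to be expected half the time. They do support asking for a marker list, adjusted p-values beside the raw ones, and a clearer power statement.

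**What to change.** In section 10.2, Exploratory Endpoints:
1. List the RT-PCR and staining markers that will be tested.
2. Report Benjamini-Hochberg adjusted p-values beside the raw p-values and confidence intervals across that list, and separately across array transcripts if these are tested.
3. Describe markers that are significant only before adjustment as hypothesis-generating.
4. Add *per marker, unadjusted* to the power statement, here and in the Study Summary.
5. In the same edit, reconcile the 14-fold figure given for both sample sizes in section 10.2 with the 8-fold figure for 8 participants in the Study Summary. The plan's own interval widths reproduce the latter.

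Do not make the adjusted threshold a condition for reporting a marker as changed, because the loss of power shown above is large for a pilot of this size.

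The cost is a few sentences and a little more analysis work, with no extra samples, visits or subjects. Fewer markers will be presented as established.

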10.3 Blinding

No blinding will occur or be necessary. All patients will receive the same treatment plan.

10.4 Subject Disposition

The disposition of subjects will describe the number of subjects enrolled, the number of subjects treated, and the number of subjects withdrawn prematurely from the study (including the reasons).

10.5 Handling of Dropouts and Missing Data

The last available SALT scores will be used to determine percent hair regrowth for dropouts and subjects who were lost to follow-up.

11. DIRECT ACCESS TO SOURCE DATA/DOCUMENTS

11.1 Overview

To decrease variability in this study any manual measurements such as SALT scoring should be done as consistently as possible, and be performed by the same individual performing the original assessments. Photographs will be taken to verify measurements, if needed.

11.2 Reporting and Recording of Data

Case Report Forms (CRF) will be developed and supplied by the University of Minnesota Department of Dermatology and will involve laboratory values and other assessments.

A CRF will be completed for each subject enrolled under this protocol. Information collected must be verifiable in the source documents. Source documents for this trial will include hospital records, clinic records, and any study-specific worksheets. Subject medical records will contain reference to the study title and assigned subject identification number. The signed consent form

must be filed with the subject's medical record.

CRF completion will be kept current to reflect subject status during the course of the trial and will be completed in a neat and legible manner to ensure accurate interpretation of data.

Study subjects will be identified by subject ID number, initials, and date of birth.

Results from the study will be available on clinicaltrials.gov. If a participant contacts us wanting additional information regarding results, we will provide them with this information.

12. ETHICAL CONSIDERATIONS

12.1 Informed Consent

The informed consent document will be used to explain in simple terms, before the subject is entered into the study, the risks and benefits to the subject. The informed consent document will contain a statement that consent is freely given, that the subject is aware of the risks and benefits of entering the study, and that the subject is free to withdraw from the study at any time.

The final IRB-approved documents must be provided to the University of Minnesota and Sponsors for regulatory purposes.

The Investigator is responsible for seeing that informed consent is obtained from each subject or legal representative and for obtaining the appropriate signatures and dates on the informed consent document prior to the performance of any protocol procedures and prior to the application of topical DPCP ointment formulation, or collection of serum samples and scalp biopsy specimens.

As used in this protocol, the term "informed consent" includes all consent given by subjects or their legal representatives.

12.2 Institutional Review

The University of Minnesota Institutional Review Board will approve the protocol and informed consent document and, if appropriate, agree to monitor the conduct of the study and agree to review it periodically. The Investigator will provide the IRB with documentation demonstrating that the IRB has approved the study before the study begins.

In addition, the Investigator will provide the following documentations:

- The IRB's annual re-approval of the protocol
- The IRB's approvals of any revisions to the informed consent document or amendments to the protocol

12.3 Ethical Considerations

The study will be conducted in accordance with the ethical principles stated in the most recent version of the Declaration of Helsinki or the applicable guidelines on Good Clinical Practice; whichever affords the greater protection to the individual.

12.4 Data Integrity Monitoring

A CTSI monitor will be used to review the study binders every 6 months while we are actively recruiting and enrolling participants. The objective of the monitor will be to ensure completion of forms including adverse event forms, reporting, and to assess for other protocol deviations. The monitor will be expected to write a report of major and minor protocol deviations and provide to the study staff.

15. FINANCING AND INSURANCE

Considerations will be provided by the University of Minnesota Department of Dermatology fund for Graduate Research and the National Alopecia Areata Foundation.

APPENDIX A: Flowchart of Study Procedures

Week(s)	>= -2		-1		0		1		2		3		4		5		6		7		8		9		10		11		12		13		14		15		16		17		18		20	
Visit(s)	1 ^a	2	3 ⁿ	4	5	6-7 ^b	8-9	10-11	12	13	14-15	16-17	18-19	20	21	22-23	24-25	26-27	28	29	30-31	32-33	34-35	36	37	38-39	40	41	42															
Study Event	Screening	Baseline, Sensitization	Dose	Challenge	Treatment										Assessment		Treatment										Assessment		Treatment										Assessment	Treatment	Assessment	Suture Removal		
Informed Consent	X																																											
Review of Inclusion and Exclusion Criteria	X	X																																										
Document Interim Medical Hx/Adverse Experiences		X	X	X	X	X	X	X	X	X	X	X	X	X	X	X	X	X	X	X	X	X	X	X	X	X	X	X	X	X	X	X	X	X										
Vital Signs	X	X			X										X																	X		X										
SALT Score	X	X	X												X																	X		X										
Physician Assessment of Alopecia		X	X												X																	X		X										
Subject Hair Loss Assessment ^s			X																																X									
Skin Biopsies ^c		X			X																															X ^d								
Phlebotomy ^e		X			X																															X ^d								
Suture Removal ^f				X		X ^g																														X ^h								
Photography		X	X	X											X									X									X		X									
Drug Application		X ⁱ	X ^j	X	X	X	X	X	X	X	X	X	X	X	X	X	X	X	X	X	X	X	X	X	X	X	X	X	X	X	X	X	X											
Assessment of Sensitization			X	X																																								
Demographic & Baseline Assessment	X																																											
Laboratory Tests ^{k,l}	X ^{k,l}																																					X ^l						
Pregnancy Test ^m	X	X													X								X									X		X										

^a Screening visit can but does not have to occur concurrently with sensitization/baseline.

^b Subjects treatment visits twice per week for 18 weeks after the challenge visit.

^c Scalp skin biopsies will be performed at baseline, 3 days after the first treatment administration, at the time of hair regrowth (if $\geq 50\%$) **OR** after the final treatment administration

^d 3rd biopsy and phlebotomy collection will occur at Visit 41 **OR** a prior date at the time of regrowth (if $\geq 50\%$)

^e Whole blood, serum collection

^f Sutures will be removed 10-14 days after the biopsy procedure

^g Of Visits 6-7, suture removal will only take place on Visit 6

^h Suture removal will occur at Visit 41 **OR** at a prior visit 10-14 days after the time of regrowth (if $\geq 50\%$)

ⁱ Drug sensitization procedure

^j Dose determination procedure

^k Pre-treatment labs include TSH, HgB, and Vitamin D

^l Safety monitoring labs include hemoglobin, hematocrit, platelets, WBC, sodium, potassium, chloride, bicarbonate, BUN/urea, total protein, albumin, alkaline phosphate, AST (SGOT), ALT (SGPT), calcium, CRP

^m Women of child bearing potential only

ⁿ See following schedule of events for dose determination visit(s):

Procedure	Visit			
	3 ¹	3 ²	3 ³	3 ⁴
Adverse events	X	X	X	X
Assessment of hair loss	X			
Photographs	X	X	X	X
DPCP ointment – 0.04%	X			
DPCP ointment – 0.08%		X		
DPCP ointment – 0.12%			X	
DPCP ointment – 0.2%				X

1: DPCP ointment 0.04% concentration is the starting concentration for all participants

2: DPCP ointment 0.08% will only be applied if participant does not have a strong enough response to the 0.005% concentration of DPCP. Thus, this visit will begin with an assessment of the sensitization reaction to the 0.005% dose. If there is not a strong enough response, 0.01% concentration DPCP will be applied to a different area of the inner upper left thigh in the same manner as the 0.005% dose. If the participant is a responder to the 0.005% DPCP, patient will proceed to the challenge visit (visit 4) as described above.

3: DPCP ointment 0.12% will only be applied if participant does not have a strong enough response to the 0.01% concentration of DPCP. Thus, this visit will begin with an assessment of the sensitization reaction to the 0.01% dose. If there is not a strong enough response, 0.05% concentration DPCP will be applied to a different area of the inner upper left thigh in the same manner as the 0.01% dose. If the participant is a responder to the 0.01% DPCP, patient will proceed to the challenge visit (visit 4) as described above.

4: DPCP ointment 0.2% will only be applied if participant does not have a strong enough response to the 0.05% concentration of DPCP. Thus, this visit will begin with an assessment of the sensitization reaction to the 0.05% dose. If there is not a strong enough response, 0.1% concentration DPCP will be applied to a different area of the inner upper left thigh in the same manner as the 0.05% dose. If the participant is a responder to the 0.05% DPCP, patient will proceed to the challenge visit (visit 4) as described above.

